1.3 Schedule of Activities (SoA)

The schedule of activities during the study is summarised for all participants in [Table 1](#), except the PK/PD subset of 12 participants which is summarised in [Table 2](#).

If the Coronavirus Disease 2019 (COVID-19) pandemic prevents participants from coming to the site, participants can have their study visit assessments performed remotely as judged appropriate by the investigator. This must be discussed with the sponsor before being implemented. In such a case, the investigator will perform a telemedicine visit and will make every effort, where applicable, to contact the participant's general practitioner or specialist physician to ensure all important medical information and safety event(s) occurring since the last visit are collected. Guidance on how to collect protocol-planned assessments will be provided to the investigator in a separate document. Such document will be filed in the trial master file. Independent ethics committees (IECs)/institutional review boards (IRBs) will be notified of the changes as applicable locally. Of note, as the adapted visit deviates from the regular protocol plan, the changes will be recorded as protocol deviations related to COVID-19.

Table 1 Schedule of Activities for All Participants Except the Pharmacokinetic/Pharmacodynamic Subset

Procedure	Screening		Intervention Period						EoS/EW
	End of Week	Day	Week 4	Week 8	Week 12	Week 16	Week 20	Week 24	
Visit Window	-	-	±3 days	±3 days	±3 days	±3 days	±3 days	±3 days	
Informed consent	X								
Eligibility	X	X							
Demography	X								
Medical and surgical history	X								
Physical examination [f]	X	X [a]			X				X
MRI scan [g]	X								
Disease-specific medical history	X								
Prior disease-specific treatment	X								
Body weight	X								X
Vital signs	X	X [a]	X	X	X	X	X	X	
12-lead electrocardiogram[b]	X		X						X
ECOG Score	X								
Injection triptorelin 6M		X							
Blood samples for triptorelin PK		X [a]	X	X	X	X	X	X	
Blood sample for testosterone PD [h]	X	X [a, e]	X	X	X	X	X	X	
Blood samples for PSA [h]	X	X [a, e]			X				X
Blood samples [c] laboratory safety tests	X	X [a, e]							X
Local tolerance [d]		X							
Previous (excluding disease-specific) and concomitant medication	X	X	X	X	X	X	X	X	
Adverse events	X	X	X	X	X	X	X	X	

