6M=6-month formulation, AE=adverse event, ALT=alanine aminotransaminase, AST=aspartate aminotransaminase, CRF=case report form, D=day; ECG=electrocardiography; ECOG=Eastern Cooperative Oncology Group, EoS/EW=end of study/early withdrawal, Hb=haemoglobin, M1b=distant metastasis bone(s), MRI=magnetic resonance imaging; PD=pharmacodynamic, PK=pharmacokinetics, PSA=prostate-specific antigen, WBC=white blood cell.

-
- a Assessment or blood sampling to be performed prior to study intervention injection. PK Predose sampling window (\leq 30 minutes).
 - b ECG to be assessed as clinically indicated at any other time in the study as required.
 - c Haematology (WBC, platelet count, Hb), Blood Chemistry (creatinine, glucose, ALT, AST, alkaline phosphatase, bilirubin (total and conjugated)) will be tested at the local laboratory. Glucose: fasting levels in all participants at Screening visit, fasting levels on Days 1 and 169. Fasting is not necessary for diabetic participants.
 - d Injection site to be specifically checked 2 hours \pm 15 minutes after injection for local reactions on Day 1. After Day 1, any local reaction AE to be collected on the CRF in the same manner as other AEs.
 - e Measurement of testosterone, PSA and laboratory safety tests for analysis purposes only and not for eligibility. The screening testosterone, PSA and safety laboratory test results will be used for eligibility.
 - f Complete physical examination to be performed (or brief physical examination based on investigator judgement). Participants, particularly those with M1b status, should be advised regarding clinical signs suggestive of spinal cord compression.
 - g Scan for prostate gland or the whole body, only if necessary, based on investigator's judgement. An MRI scan is not required if performed within 1 month of screening.
 - h Testosterone and PSA testing will be performed at the central laboratory.

See Appendix [10.5](#) for ECOG performance scale.

Table 2 Schedule of Assessments for the Pharmacokinetic/Pharmacodynamic Subset of Participants

Procedures	Screening	Intervention Period												EoS/EW
		-	-	-	-	-	-	-	Week 4	Week 8	Week 12	Week 16	Week 20	
End of Week	-	-	-	-	-	-	-	-						
Day	D-28 to D-1	D1	D2	D3	D5	D8	D15	D22	D29	D57	D85	D113	D141	D169
Visit Window										±3 days				
Previous (excluding disease-specific) and concomitant medication	X	X	X	X	X	X	X	X	X	X	X	X	X	X
Adverse events	X	X	X	X	X	X	X	X	X	X	X	X	X	X

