3 OBJECTIVES AND ENDPOINTS

Table 4 Objectives and Endpoints

Objectives	Endpoints
Primary	

 To evaluate the efficacy of triptorelin pamoate 22.5 mg 6-month formulation in achieving castrate levels of testosterone To evaluate the efficacy of triptorelin pamoate 22.5 mg 6-month formulation in maintaining the castrate levels of serum testosterone 	
 Percentage of participants achieving castrate levels of serum testosterone (<50 ng/dL or 1.735 nmol/L) on Day 29 Percentage of participants maintaining the castrate levels from Week 8 to Week 24
Secondary	

 To assess the safety profile including local tolerability of triptorelin pamoate 22.5 mg 6-month formulation 	
 Incidence of TEAEs (including local tolerability) throughout the study i.e., up to Week 24 Change from baseline in clinical safety laboratory parameters (blood chemistry and haematology) at Week 24 Change from baseline in physical examination at Day 1, Week 12 and Week 24 Change from baseline in ECG at Week 4 and Week 24 Change from baseline in vital signs (blood pressure and heart rate) at each visit up to Week 24

 To demonstrate the effect of triptorelin pamoate 22.5 mg 6-month formulation on PSA response 	
 Percent change in PSA from baseline (prior to injection) at Week 12 and Week 24 (percent change in PSA is defined as the absolute value of difference between the PSA values at Week 12 and Week 24 and the baseline value divided by the baseline value)

 To assess the PK of triptorelin pamoate 22.5 mg 6-month formulation in a subset of 12 participants 	
 PK parameters for dosing interval up to 24 weeks: 
 t_{max} C_{max} AUC_{0-169} AUC_{last}

 To assess the PD of testosterone in a subset of 12 participants 	
 PD parameters for dosing interval up to 24 weeks: 
 t_{max} C_{max} t_{cast}

 To assess the PK of triptorelin pamoate 22.5 mg 6-month formulation for all participants 	
 Sparse plasma concentrations of triptorelin at pre-dose and post-dose at Weeks 4, 8, 12, 16, 20 and 24

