8 STUDY ASSESSMENTS AND PROCEDURES

- Study procedures and their timing are summarised in the SoA (Table 1 and Table 2). Protocol waivers and exemptions are not allowed.
- Immediate safety concerns should be discussed with the sponsor immediately upon occurrence or awareness to determine if the participant should continue or discontinue study intervention.
- Adherence to the study design requirements, including those specified in the SoA (Table 1 and Table 2), is essential and required for study conduct.
- All screening evaluations must be completed and reviewed to confirm that potential participants meet all eligibility criteria. The investigator will maintain a screening log to record details of all participants screened and to confirm eligibility or record reasons for screening failure, as applicable.
- Procedures conducted as part of the participant's routine clinical management (e.g. blood count) and obtained before signing of the ICF may be utilised for screening or baseline purposes provided the procedures met the protocol-specified criteria and were performed within the timeframe defined in the SoA (Table 1 and Table 2)
- The maximum amount of blood collected from each participant over the duration of the study, including any extra assessments that may be required, will not exceed 95 mL for the PK/PD subset of participants and 60 mL for all other participants. Blood sampling should be taken at the same time of day during different visits.
- Repeat or unscheduled samples may be taken for safety reasons or in case of technical issues with the samples.

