9.4.5 Safety Analyses

Safety endpoints are indicated in Section 3.

All safety data will be included in the participant data listings. Analyses and summary tables will be based upon the safety set.

All AEs will be coded according to the Medical Dictionary for Regulatory Activities (MedDRA) version 24.1 (or higher if available) and will be classified by MedDRA preferred term and system organ class. Adverse event listings will be presented by participant, system organ class and PT.

The incidence of all TEAEs and SAEs will be tabulated overall. In addition, summary tables will be presented by maximum intensity and drug relationship.

A TEAE is defined as any AE that occurs during the active phase of the study (from study intervention injection to 24 weeks after injection) if it was not present prior to receiving study intervention, or:

- it was present prior to receiving IMP but the intensity increased during the active phase of the study.
- It became serious during the active phase of the study
- It was present prior to receiving the study intervention and the intensity was the same, but the causality changed to 'related to treatment' during the active phase of the study.

All TEAEs will be flagged in the AEs listings.

Haematological and biochemical toxicities will be recorded and graded according to the NCI CTCAE criteria, where available. The National Cancer Institute-Common Toxicity Criteria for Adverse Events (NCI-CTCAE) Grade 3 and 4 haematology and biochemistry variables by participant and by cycle will be listed.

Actual values and changes from baseline in clinical laboratory tests, physical examinations, vital signs and 12-lead ECG will be summarized using descriptive statistics at each visit. For laboratory data, abnormal values will be flagged in the data listings and a list of clinically significant abnormal values will be presented. Shift tables using the worst on-treatment grade will be presented for the number and percentage of participants with NCI-CTCAE grades.

AEs reported by investigators using the NCI-CTCAE classification (Version 5.0 or higher) will be coded using MedDRA Version 24.1 (or higher if available).

Summary incidence tables will be provided, classified by SOC, PT and associated NCI/CTC worst grade. In the event of multiple occurrences of the same AEs being reported by the same participant, the maximum intensity (Grade 5 >Grade 4 >Grade 3 >Grade 2 >Grade 1 >missing >not applicable) will be chosen.

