2.6 Change from Statistical Section of the Protocol

Protocol	SAP
Section 9.4.1.3 Demographic and Other Baseline Characteristics Descriptive summary statistics (n, mean, standard deviation (SD), median, minimum, maximum) or frequency counts of demographic and baseline data (medical history, concomitant disease (predosing AEs and ongoing medical history, prior medications and therapies, etc.) will be presented for the FAS, PP and safety sets.	Section 5.5 Medical history, non-drug therapies, medications and surgical procedures will be present for only Safety Set.

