- If the grade is missing for a TEAE, it will be considered as missing in the summary tables;
- Summary by grade will be presented;
- If the causality is missing for a TEAE, it will be considered related in the summary tables;
- The non-serious TEAEs table should include a specific row “any non-serious TEAE above 5%”.

In addition, a listing with all AEs data will be listed by treatment group including non-TEAEs, Treatment-emergence status will be flagged in the listing.

Deaths, SAEs, and Other Significant Adverse Events

The following summaries will be provided:

- A summary of the number and percentage of participants reporting a SAE by treatment group, SOC and PT,
- A summary of the number and percentage of participants reporting a treatment emergent SAE by treatment group, SOC and PT,
- A summary of the number and percentage of participants reporting a treatment-related SAE by treatment group, SOC and PT,
- A summary of the number and percentage of participants reporting a SAE by treatment group, maximum CTCAE grade, SOC and PT,
- A summary of the number and percentage of participants reporting a SAE by treatment group, maximum causality, SOC and PT,
- A summary of the number and percentage of participants with TEAEs leading to discontinuation of study by treatment group, SOC and PT,
- A summary of the number and percentage of deaths (including SAEs with fatal outcome and deaths as PT) including primary reasons for death.

AEs of special interest is not applicable.

The following listings will be provided:

- A listing of all deaths that occurred during the study,
- A listing of all SAEs.
- A listing of TEAEs leading to discontinuation of study.

5.8.4 *Laboratory Data*

All laboratory data (Hematology and Clinical Chemistry) will be presented in the units of International System of Units (SI).

The following summaries will be provided:

- A summary of the actual and change from baseline in each laboratory parameter by treatment group and visit,
- A shift from baseline to each post-baseline timepoints of the number and percentage of participants experiencing low, normal or high values, by laboratory parameter,
- A shift from baseline to end of study according to Common Toxicity (CTC) grading system (Version 5.0 or higher),

For shift tables, the denominator should be the number of participants with both a baseline and a post-baseline assessment at a given timepoint.

In addition, the following listings are to be provided:

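### SAP 5.8.4 replaces the protocol's worst-grade laboratory shift table with a baseline-to-end-of-study shift and does not declare the change

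*SAP*

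**What the plan says.** Protocol 9.4.5 (Safety Analyses) states: "Shift tables using the worst on-treatment grade will be presented for the number and percentage of participants with NCI-CTCAE grades".

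SAP 5.8.4 (Laboratory Data) lists instead: "A shift from baseline to end of study according to Common Toxicity (CTC) grading system". No other table in that section uses a worst laboratory grade. The second shift table there classifies values as low, normal or high at each post-baseline timepoint and carries no CTC grade. For all shift tables, the denominator is restricted to participants with a baseline value and a value at the timepoint in question.

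SAP 2.6 is the place for departures from the protocol's statistical section. Its only entry concerns other data: "Medical history, non-drug therapies, medications and surgical procedures will be present for only Safety Set".

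**The concern.** The two documents define different tables under the same purpose. A worst-grade shift answers how bad a laboratory value became at any time after dosing. An end-of-study shift answers how it stood at the last visit. The SAP is meant to add detail to the protocol's analyses, and here it substitutes one safety table for another without saying so.

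What is at stake is the count of participants by worst laboratory grade. If an abnormality is found on an extra test and has improved by the last visit, the end-of-study table shows the better grade. Protocol 8.3.5 makes that pattern plausible, because clinically significant abnormal values are to be retested until they normalise, return to baseline or cease to matter clinically.

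**Working it through.** The plan gives no figure to reproduce here. The check is a count of draws, followed by a comparison of the two table rules case by case.

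**1. Scheduled safety draws.** The row "Blood samples [c] laboratory safety tests" in Protocol Table 1 carries three marks: Screening, Day 1 and EoS/EW. Day 1 carries footnote a ("Assessment or blood sampling to be performed prior to study intervention injection"), so it is a baseline sample. The glucose footnote names the same three occasions ("fasting levels in all participants at Screening visit, fasting levels on Days 1 and 169"). The endpoint in Protocol 3 has one post-dose timepoint: "Change from baseline in clinical safety laboratory parameters (blood chemistry and haematology) at Week 24". Scheduled post-dose draws per participant: 3 − 2 = 1.

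**2. Cross-check on blood volume.** Protocol 8 says the total "will not exceed 95 mL for the PK/PD subset of participants and 60 mL for all other participants". Protocol 8.5 gives 14 mL for PK (40 mL in the subset), Protocol 8.2 gives 26 mL for testosterone and PSA (38 mL in the subset), and Protocol 8.3.5 gives 2 + 3 = 5 mL per safety draw.

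| Group | 3 draws | 4 draws | Cap |
|---|---|---|---|
| All others | 14 + 26 + 15 = 55 mL | 14 + 26 + 20 = 60 mL | 60 mL |
| PK/PD subset | 40 + 38 + 15 = 93 mL | 40 + 38 + 20 = 98 mL | 95 mL |

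A fourth planned draw would break the cap in the subset. It would only just reach the cap in the others, so this supports the three-draw reading without proving it. In the text available to me, the Table 1 columns are out of alignment and the laboratory row of Table 2 is not shown. The count therefore rests on the Table 1 row, the footnotes, the endpoint and these volumes. Table 6 marks the intervention period without naming days, which fits the Day 1 draw.

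**3. The two rules compared.** Let g(E) be the grade at EoS/EW and g(U) the worst grade on any unscheduled or repeat post-dose test.

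| Post-dose data | SAP table | Worst-grade table | Same? |
|---|---|---|---|
| EoS/EW only | g(E) | g(E) | Yes |
| Both, g(U) ≤ g(E) | g(E) | g(E) | Yes |
| Both, g(U) > g(E) | g(E) | g(U) | No |
| Unscheduled only | excluded | g(U) | No |
| None | excluded | excluded | Yes |

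On scheduled data alone, 0 participants change cell. Extra tests are possible: Protocol 8 allows unscheduled or repeat samples for safety, and Protocol 10.2 allows additional tests at any time.

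**4. Size.** The documents give no rate of unscheduled testing. As an assumption only, suppose 5% to 20% of 195 participants have an unscheduled post-dose test, and 25% to 50% of those show a higher grade than at EoS/EW:

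- low end: 195 × 0.05 × 0.25 = 2.4
- high end: 195 × 0.20 × 0.50 = 19.5

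That is about 2 to 20 participants. The range shows how the answer depends on the assumptions and is not an estimate. The unscheduled-only row cannot be sized either. Planned dropout leaves 195 − 165 = 30 participants, but Protocol 7.2 asks for an early discontinuation visit, and the number who would miss that sample is not given.

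**The case against.** A reader might infer that any toxicity resolving by Day 169 vanishes from the table, or is reported as no toxicity. The documents do not support that. With no scheduled draw between the pre-dose sample and EoS/EW, most transient changes would never be measured under either rule; that follows from the visit schedule, not from the SAP table. An affected participant appears at the end-of-study grade, which need not be zero. For early withdrawals the comparison point is the withdrawal visit, not Day 169.

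The defence can also say that much stays visible:

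- SAP 5.8.4 lists all laboratory data and all abnormal data, and SAP 6.2 puts retests and unscheduled visits in every listing. Grade 2 values therefore appear even though the separate Grade 3-and-above listing does not select for them.
- Clinically significant changes are recorded as adverse events (Protocol 8.3.5), and SAP 5.8.3 tabulates treatment-emergent events by maximum grade.
- The end-of-study table matches the Week 24 laboratory endpoint.
- Protocol 9.4.5 does not say that unscheduled tests feed its shift table. Including them is the natural reading of a worst grade, but it is a reading.

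All of this stands, and it limits the consequence. It does not remove the mismatch. Listings give individual values, not the number and percentage that the protocol promised. The adverse event tables depend on the investigator's judgement of clinical significance, and Protocol 8.3.5 by default does not count findings tied to the underlying disease. The low/normal/high shift has no grades, and SAP 6.2 limits by-visit tables to scheduled visits. No planned output gives counts by worst laboratory grade independent of that judgement.

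**Conclusion.** The point holds as an undeclared inconsistency between SAP 5.8.4 and Protocol 9.4.5, with a limited effect. The tables are identical on scheduled data. They part only for participants whose unscheduled or repeat test is worse than their EoS/EW sample, and for those with an unscheduled post-dose test but no EoS/EW sample. The number affected is unknown and probably small. This rests on the three-draw reading of the schedule and on reading the protocol's worst grade as including unscheduled tests. The co-primary analyses are not touched. It is a minor point, worth correcting because the correction is nearly free.

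**What to change.** In SAP 5.8.4, change the CTC table to baseline versus worst post-baseline grade, including unscheduled and repeat tests. Set its denominator to participants with a baseline and at least one post-baseline value. SAP 6.2 already allows unscheduled values to supply a worst value, so no new data rule is needed. Build the table by CTCAE term, since SAP Appendix A6 grades some analytes, such as glucose and haemoglobin, in both directions.

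If the end-of-study shift is also kept, list it in SAP 2.6. If the sponsor prefers the end-of-study shift alone, the minimum is to declare and justify that departure in SAP 2.6.

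The cost is one line in the SAP and one adjusted table shell. No new samples, visits or participants are needed.

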5.2 Exclusion Criteria

Participants are excluded from the study if any of the following criteria apply:

Medical conditions

1. Risk of a serious complication in the case of tumour flare (known or suspicion of vertebral metastases threatening spinal cord compression or significant obstructive uropathy).
2. Presence of another neoplastic lesion or brain metastases.
- 3a. Previous history of QT prolongation or concomitant use of medicinal products known to prolong the QT interval or with a known risk of torsades de pointes.
- 4a. Metastatic hormone-sensitive prostate cancer with high tumour burden.
(Note: high tumour burden: presence of visceral metastases and/or at least four bone lesions with at least one lesion outside the vertebral column and/or pelvis per CHAARTED study (Kyriakopoulos 2018).)

5. Metastatic castration-resistant prostate cancer.

Prior/concomitant therapy

6. Previous surgical castration.

- 7a. Previous hormone therapy (including abiraterone) for prostate cancer within 6 months prior to study screening.
- 8a. Previous cytotoxic chemotherapy treatment within 6 months prior to study screening.
- 9a. Use of finasteride or dutasteride within 2 months prior to study screening.
10. Previous hypophysectomy or adrenalectomy.
- 11a. Any current use or use within 6 months prior to treatment start of medications which are known to affect the metabolism and/or secretion of androgenic hormones: ketoconazole, aminoglutethimide, oestrogens and antiandrogens.
Note: antiandrogen: enzalutamide, apalutamide or darolutamide is allowed (if required per investigator's clinical judgement) due to no interference on the metabolism and/or secretion of androgenic hormones.
- 12a. Current use of systemic or inhaled corticosteroids (topical application permitted).
13. Any previous use of traditional Chinese medicine or herbal products within 1 month prior to study screening or planned use during the study of products, which are known to have cytotoxic effect or affect the metabolism and/or secretion of androgenic hormones.

Prior/concurrent clinical study experience

- 14a. Participation in another study with an investigational drug or treatment within 3 months prior to study screening or within 5 drug half-lives of the investigational drug (whichever is the longer).

Diagnostic assessments

15. Severe kidney or liver impairment (creatinine >2 x upper limit of normal (ULN), aspartate aminotransferase (AST) and alanine aminotransferase (ALT) >3 x ULN).

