- A listing of all laboratory data. Out-of-reference-range values will be flagged as high (H) or low (L),
- A listing of all abnormal data.
- A listing of CTCAE grade 3 and higher values. All data for a laboratory parameter will be displayed for a participant who has any post-baseline value with CTCAE grade greater than or equal to 3 for the parameter.

5.8.5 ***Vital Signs***

Blood pressure, temperature, respiratory rate and heart rate will be assessed. Any clinically significant vital signs will be recorded as AEs. The following summaries are to be provided:

- A summary of the actual and change from baseline in each vital sign parameter by treatment group and visit,
- A shift from baseline to post-dose in interpretation of clinical significance (normal, abnormal, not clinically significant [NCS], abnormal, clinically significant [CS]).

The following listing are to be provided:

- A listing of vital sign data.
- Listing of all abnormal data.

5.8.6 ***Electrocardiogram (ECG)***

Results from the local lab units will be used.

The following quantitative ECG measurements will be taken during the study:

- heart rate (bpm),
- RR interval (msec),
- PR interval (msec),
- QRS interval (msec),
- QT interval (msec),

Fridericia corrected QT (QTcF) interval (msec) = $QT/\sqrt[3]{RR}$;

An overall Investigator assessment of ECG will be provided as “normal”, “abnormal NCS” and “abnormal CS”. Any clinically significant abnormalities will be recorded as AEs.

The following summaries of ECG data may be appropriate:

- A summary of the actual and change from baseline in each ECG parameter by treatment group and visit,
- A shift from baseline (normal vs. abnormal NCS vs. abnormal CS) to each post-baseline visit.

The following listing are to be provided:

- A listing of ECG data.
- A listing of all abnormal data.

5.8.7 ***Physical Examination***

The following summary and listings will be provided:

- A shift from baseline (normal vs abnormal NCS vs. abnormal CS) to each post-baseline visit by body system.
- A listing with any participants with at least one physical examination abnormality.

5.8.8 *Other*

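### The SAP's QTcF formula omits the conversion of RR from milliseconds to seconds, so QTcF derived as written is one tenth of its proper value

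*SAP*

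**What the plan says.** SAP 5.8.6 lists the quantitative ECG measurements with their units, among them "RR interval (msec") and "QT interval (msec"). It then gives QTcF its own line with an equation: "Fridericia corrected QT (QTcF) interval (msec") is set equal to QT over the cube root of RR, with the result labelled in milliseconds. The equation has no factor of 1000, and nothing in the section says that RR is to be in seconds. The only other remark on units there is "Results from the local lab units will be used", which converts nothing. SAP section 7, on derived data, has no content that could supply a conversion.

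The planned ECG output is "A summary of the actual and change from baseline in each ECG parameter by treatment group and visit", together with a shift table of the investigator's overall assessment. In Protocol section 3 the matching secondary safety endpoint is "Change from baseline in ECG at Week 4 and Week 24". Protocol 8.3.3 names RR, PR, QRS, QT and QTcF as intervals that can be measured automatically from the single 12-lead ECG.

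**The concern.** The formula and the units listed just above it do not fit together. A programmer who takes RR in milliseconds from the database and applies the equation will get QTcF values of about 40 where about 400 is expected.

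QTcF is also the ECG parameter closest to a concern the protocol itself raises. Exclusion criterion 3a covers "Previous history of QT prolongation or concomitant use of medicinal products known to prolong the QT interval", and Protocol 6.8 bars QT-prolonging drugs during the study. If the formula is followed, a real prolongation would appear in the change-from-baseline table at one tenth of its size, and a change of a few milliseconds does not look wrong on its face.

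**Working it through.** **Inputs.** The QTcF equation, the unit of RR (msec), the unit of QT (msec) and the labelled unit of QTcF (msec) all come from SAP 5.8.6. The documents give no numerical QTcF value to reproduce, so the QT and RR values below are illustrative assumptions. The ratio between the two results does not depend on them.

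**Step 1: units.** With both inputs in msec, QT / RR^(1/3) has the unit msec / msec^(1/3) = msec^(2/3). That is not the msec on the label.

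**Step 2: reference point.** The formula leaves QT unchanged when RR = 1. An RR of 1 second is a heart rate of 60 / 1 = 60 beats per minute, a sensible reference. An RR of 1 msec would be 60,000 beats per minute. So the formula is meant for RR in seconds. At RR = 1000 msec the corrected value should equal QT, but the formula as written returns QT / 1000^(1/3) = QT / 10.

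**Step 3: size of the error.**
- As written: A = QT / RR^(1/3), RR in msec.
- With RR in seconds: B = QT / (RR/1000)^(1/3).
- B / A = 1000^(1/3) = 10 for any QT and RR.

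| QT (msec) | RR (msec) | A, as written | B, RR in seconds | B / A |
|---|---|---|---|---|
| 400 | 800 | 43.1 | 430.9 | 10 |
| 400 | 1000 | 40.0 | 400.0 | 10 |
| 380 | 800 | 40.9 | 409.3 | 10 |
| 440 | 1200 | 41.4 | 414.1 | 10 |
| 360 | 600 | 42.7 | 426.8 | 10 |
| 450 | 750 | 49.5 | 495.3 | 10 |

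**Step 4: change from baseline.** Take QT/RR of 400/900 msec at baseline and 420/1000 msec at follow-up.
- As written: 42.00 − 41.43 = +0.57.
- With RR in seconds: 420.00 − 414.30 = +5.70 msec.

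The factor is constant, so it carries over to every absolute change: a true rise of 60 msec becomes 60 / 10 = 6 msec. A percent change is unaffected (1.38% either way), but SAP 5.8.6 plans actual values and changes from baseline, not percent changes.

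**The case against.** The arithmetic is not in dispute. The case on the other side is about whether the error would reach the reported results, and how much it would matter.

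- **Source of QTcF.** Protocol 8.3.3 lists QTcF with the automatically measured intervals. If the device value is summarised, the formula is never used. An empty derived-data section in the SAP fits that reading, and the layout of the QTcF line is weak evidence because the equation may have been displaced when the text was extracted. This stands in part: the documents do not settle the source. But an explicit equation in the SAP points to a derivation, and a possible alternative source does not correct the equation.
- **Detection.** A QTcF near 40 msec beside a QT near 400 msec is implausible and would probably be noticed. That is fair for the actual values. It is less reassuring for the change column, where small numbers are expected.
- **Other safeguards.** The investigator's normal/abnormal assessment, its shift table, adverse event reporting and the summaries of uncorrected QT and RR do not use the formula. No eligibility or stopping rule uses a QTcF value, and no QTcF threshold table is planned. The ECG analysis is descriptive. All of this stands and limits the weight of the point.
- **Recoverable intent.** The method is named and the output unit is given, so an experienced programmer could infer that RR must be in seconds. That is true, but a correct result then depends on someone departing from the written plan.

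**Conclusion.** The formula is wrong as written. Applied to the units the SAP lists, it gives QTcF values and absolute changes from baseline that are exactly ten times too small, for every record. The factor rests only on the stated units and equation, not on any assumed ECG values.

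The effect on the study report is conditional. It arises if QTcF is derived from this line with RR left in milliseconds, and not if the device value is used or RR is converted. The investigator-assessed ECG shift table, the adverse event data, the co-primary endpoints and the sample size are untouched. It should be corrected because it concerns a parameter within a stated secondary safety endpoint, but it does not threaten the main conclusions of the trial.

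**What to change.** In SAP 5.8.6, replace the equation with: QTcF (msec) = QT (msec) / cube root of (RR (msec) / 1000).

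Add one sentence saying whether the summarised QTcF is this derived value or the device value under Protocol 8.3.3. If it is the device value, say that the formula serves only to fill gaps or check values, with RR in seconds.

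This costs a line or two of SAP text, needs no new data and has no downside. It is best done before database lock, because the SAP introduction requires departures from the SAP after lock to be documented in the study report.
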